3.4. INFORMED CONSENT

Consent for the SEARCH Study is handled through three important mechanisms under the supervision of local IRB(s). Individual differences exist based on requirements of local IRBs. In general: 1) initial data for the Registry Study is collected (without participant contact) under a HIPAA waiver; 2) completion of surveys (either by mail or web-based/online) is covered by a waiver of documentation of consent [aka, implied consent] according to local IRB requirements in the Registry and Cohort Studies; and 3) written informed consent is obtained prior to all IPVs in the Registry and Cohort Studies.

As in previous phases of SEARCH, the initial data collection in the Registry Study (case ascertainment) is covered by a HIPAA waiver. That is, identification of all new cases of diabetes in a defined geographic area or health plan does not require that registered cases provide written or implied informed consent; HIPAA requirements are waived.

Mailed and/or web-based online surveys are utilized in both the Registry Study and Cohort Study. In this case, consent is implied with completion of the surveys. In the Registry Study, potentially eligible cases are mailed (or emailed with internet link) an introductory letter that gives a brief description of the research study along with the Initial Participant Survey (IPS). For individuals who are less than 18 years of age, the introductory letter is mailed to a parent or guardian. If the completed IPS is not returned and the participant does not refuse after receiving the introductory letter, a member of the local research team may call the individual or the parent to complete the IPS. Again, consent requirements for completion of the IPS are governed by the local IRB. In the Cohort Study, a subset will be asked to participate in the survey-only group, for which surveys will be mailed (or emailed with internet link) for completion at home.

Written informed consent is obtained for all individuals/parents who agree to participate in the Registry Study IPV as well as for the Cohort Study IPV in accordance with local IRB requirements. If the participant is less than 18 years of age, the parent or guardian must give written informed consent prior to the initiation of any study procedures or data collection, according to the requirements of the local IRB. Written assent of participants who are less than 18 years of age is also governed by the requirements of the local IRB. If the participant is 18 years of age or older, the participant must give written informed consent. Copies of completed consent forms are maintained in the participant's local research record.

There are three optional components to the written informed consent: storage of serum/plasma/urine and DNA/miRNA; transfer of data and samples to the NIDDK Repository; and sharing of data and genetic information with dbGaP (database of Genotypes and Phenotypes). In each case, participants or their parent must indicate in writing whether or not they are providing consent for these optional components. The NIDDK Central Repository is a research resource supported by the National Institutes of Health. At the end of the SEARCH, de-identified research data and samples of blood and urine will be provided to the Repository for participants who have consented to this component. For all optional components, participants may choose to participate in SEARCH but not provide consent to participate in these components.

3.5. RECRUITMENT & RETENTION

The SEARCH Registry Study sites continue to employ a wide variety of methods shown to be highly effective at recruiting study participants for the IPS and IPV. Recruitment strategies have included meeting the family at a medical appointment to introduce the study; mailing study brochures and other informational letters; posting study materials in clinics; enlisting the encouragement by diabetes care providers; emailing, texting, or using social media such as Facebook to contact potential participants; phoning participants to complete the surveys and/or schedule a visit; offering online surveys; and one or more reminder calls prior to the scheduled visit. Participation in the IPV is facilitated by flexible weekday appointments, as well as Saturdays, satellite clinics, and home visits. Sites offer to pair research visits with clinical appointments when possible; provide transportation and/or lodging; and generally assist participants with removing barriers to study participation.

Study participants are offered remuneration that is appropriate for the length and burden of the study visit. Participants and their providers receive the clinically-relevant research laboratory test results, which may assist with their clinical care. To retain Registry Study participants for future studies and to share study progress, we utilize traditional, proven, retention strategies including: birthday cards, study newsletters, updating contact information annually, and utilizing internet-based search systems to locate individuals lost to follow-up.

Similarly, the SEARCH Cohort Study has maintained outstanding participant retention throughout its history. We continue to employ traditional, proven, retention strategies as described above. We also offer flexible study date appointments including home visits, offer assistance with transportation, mail pre-visit instructions, one or more reminder calls prior to the scheduled visit, provide acknowledgement of participation, and provide participant remunerations that are appropriate for the length and the respondent burden of the proposed study visit. Investigators and study personnel also continue to solicit the support of diabetes providers to encourage on-going study participation. Communications with providers include letters, e-mail messages, telephone calls, newsletters, individual discussions, and group presentations of study goals and preliminary results.

4. Study Measurements

For SEARCH phases 1-3, all clinical sites have operated under a common protocol. This approach is followed in SEARCH 4 Registry and Cohort Studies as well. That is, data from each site is obtained, managed, and protected according to a standard study protocol that has been developed and vetted by the Steering Committee and approved by all participating IRBs and by the NIDDK Observational Studies Monitoring Board (OSMB). Clinic sites use a standard informed consent template, modified as needed by local IRB requirements. All clinic staff are trained and certified, operate under a single Manual of Procedures (MOP), and follow a standard set of data collection procedures. Clinic staff participate in both central and local training as needed. Clinical Center investigators and staff participate in ongoing working groups and established study committees to ensure that identical procedures are followed at each site for the purpose of recruitment, retention, and ensuring the highest quality of study data.

4.1. MEASUREMENTS - REGISTRY STUDY

Centers in the SEARCH Registry Study continue to conduct population-based ascertainment of cases of diabetes in youth < 20 years of age using methods consistent with those employed in SEARCH 1-3. This involves identification, case validation, confirmation of eligibility, deduplication, and registration of cases centrally with the SEARCH Coordinating Center. There are three aspects of data collection in the Registry Study: 1) data obtained from all potential registered cases; 2) the Initial Participant Survey (IPS); and 3) data obtained during an in-person visit (IPV) on a subset of the 2016 registered cases.

Collection of Data on all Registered Cases: A minimum amount of demographic and clinical information is needed for all cases in order to calculate population-based incidence

rates and prevalence of diabetes mellitus by age, sex, diabetes type and race/ethnicity. The primary source of this information is the medical record except for race and Hispanic ethnicity, which, when obtained by self-report using the IPS, supersedes the report via medical record. Study staff abstract information from the medical record for the period from diabetes diagnosis to six months after this date to obtain the following information: 1) date of birth, 2) sex, 3) race/ethnicity, 4) diagnosis date, 5) zip code at diagnosis, 6) county and state of residence at diagnosis, 7) diabetes type at the time of diagnosis and the diabetes type reported closest to 6 months, 8) whether diabetes autoantibodies were measured up to 6 months after diagnosis [GAD/GAA, IA2/ICA512, ICA, IAA, and ZnT8], 9) height, 10) weight (closest to diagnosis), 11) whether the participant ever used insulin, 12) whether insulin was discontinued, 13) presence of acanthosis nigricans, and 14) whether DKA was noted (with dates, bicarbonate, pH, and glucose values). For potential cases not eligible for registration, minimal demographic data are maintained in order to facilitate validation and de-duplication of local cases.

Initial Participant Survey (IPS): All registered cases are invited to complete the IPS. The IPS is used to: a) verify case eligibility (e.g., residence in the year of diagnosis); b) obtain self-reported race/ethnicity and selected clinical and demographic information; and c) introduce participants to SEARCH to facilitate future studies. The IPS queries symptoms at presentation, potential secondary causes of diabetes, use of insulin and other medications, diabetes treatment history, height and weight, family structure, usual language spoken, type of health insurance, usual provider for diabetes care, highest parental education, household income, nativity of person with diabetes and their parents, and contact information. All registered cases are eligible to complete the IPS online, by mail, or by interviewer administration by telephone or in person.

In-Person Visit (IPV): A sample of registered cases diagnosed in 2016 will be invited to an IPV. The IPV enables an analysis comparing agreement between provider assigned diabetes type compared to SEARCH etiologic type in order to interpret the potential meaning of trends over time according to provider type, and to enable statistical adjustment for differences in agreement over time. The IPV, lasting approximately 60 minutes, includes collection of fasting blood (3 TBSP) and urine samples, a brief physical examination, and a medication inventory, all conducted under SEARCH standardized protocols and described below for the Cohort Study. Measurements made to inform dimensions of diabetes type include diabetes autoimmunity (GAD65, IA-2, and ZnT8 antibodies), and the SEARCH validated insulin sensitivity index (waist circumference, HbA1c, and triglycerides) (15). We will also measure markers of kidney function (albumin and creatinine from a first morning void, cystatin-c and serum creatinine), the latter two measures pending availability of funds. To facilitate work that requires additional funding in the future, we will store plasma, serum, DNA, and urine. Specimens are processed locally and shipped within 24 hours to the central

laboratory. Diabetes autoantibodies are measured by standardized protocol and a common serum calibrator developed by an NIDDK- sponsored standardization group.

4.2. MEASUREMENTS - COHORT STUDY

The study visit for the cohort study participants is expected to take approximately four hours and includes physical measures and questionnaires. A parent/guardian is required to attend if the individual with diabetes is < 18 years old. Most of the measures obtained during the SEARCH 4 visit are the same as to those obtained in previous visits. New measures, particularly cardiac echocardiography and neurocognitive testing, are noted in Table 4, along with data obtained at C0 (baseline visit), intermediate visits (12, 24, 60 months), and the SEARCH 3 Cohort visit (C1).

Surveys. SEARCH has included surveys in multiple domains over time. Surveys in SEARCH 4 include:

- a) Health history including pregnancy history of women;
- b) Treatment including all prescribed medications, insulin regimens and glucose monitoring devices (19,20);
- c) Behavioral factors including diet (21), physical activity (22), TV and computer use (23), smoking (24), and substance use (25);
- d) Psychosocial factors using CES-D scales (26-28), the PROMIS and PHQ9 depression and anxiety screening tools (29), Hypoglycemia Fear Survey (HFS-C,P) (30-33), the updated Diabetes Responsibility and Conflict Scale to assess diabetesspecific family conflict (34); Stigma and Discrimination. Diabetes self-care is assessed with the Diabetes Self-Management Questionnaire (DSMQ) (35);
- e) Socio-cultural factors including household and per capita income, family structure, preferred language, migration status, parental and participant attained education, participant employment status, household food security;
- f) Processes of care including type and frequency of utilizing health care providers, processes of diabetes self-management training, and recent hospitalizations (36);
- g) Quality of care based on ADA guidelines for pediatric diabetes care in terms of testing frequency for HbA1c, blood pressure, lipids, urine albumin, retinopathy screening, and foot checks (37). Receipt of services is measured by self-report by parents (participant age <18) or adult participants (age >18 yrs.);
- h) Quality of life using the Pediatric Quality of Life Inventory (PedsQL) (38-40) with age-specific and parental scales for participants < 18 years and validated scales for young adults 18-25 and over 26;
- i) Barriers to care via items from the Consumer Assessment of Healthcare Providers and Systems survey (CAHPS 3.0) Supplemental Item Set for Children with Chronic

Conditions. Additional information about continuity of health insurance, continuity of care, cost-related non-adherence and financial burden is collected using the following surveys, adapted for youth and young adults: Medical Expenditure Panel Survey (MEPS) [Agency for Healthcare Research and Quality (AHRQ)]; Perceived Financial Burden of Diabetes and Cost-related Medication Non-adherence (41);

j) Transition to adult care: Specific questions about processes of care, motivations, satisfaction with, and preparation for transition from pediatric to adult care, adapted from validated measures that have been developed to assess patients' perceptions of other kinds of care transition, such as the Care Transition Measure (42). We will also measure care transition planning by adapting items from the National Survey of Children with Special Health Care Needs.

Physical exam. Standardized anthropometry methods include height, weight, waist circumference (using NHANES and WHO protocols); systolic and diastolic blood pressure; and evaluation for acanthosis nigricans.

Laboratory parameters. Fasting blood (3 TBSP) and first morning urine are collected following standard protocols. Blood and urine laboratory parameters continue to be measured using established protocols at the Northwest Lipid Research Laboratory. Samples are shipped from clinical centers to the central laboratory. Results are sent from the laboratory to the CC through established secure protocols.

Cardiac echocardiography. Measures of cardiac structure and function are obtained using cardiac echocardiography in a subgroup of Cohort Study participants. Measures include two dimensional (2-D) directed M-mode echo images to determine left ventricular mass (LVM), left atrial size and relative wall thickness, as well as shortening fraction, LV strain and diastolic function. The primary outcome measure is LVM determined by 2-D guided M-mode echo at end diastole (43, 44) using the autopsy corrected equation of Devereux (45). Echocardiograms are read on a Digiview instrument and strain is read on a Tomtec instrument. Digital images recorded on CDs identified only by participant ID number are sent to Cardiovascular Reading Center.

Retinal Photography. We will continue obtaining retinal images using Canon CR-1 Mark II fundus cameras. Consistent with NHANES protocol (46), two 45-degree images are taken of each eye: one centered on the optic nerve and the other on the fovea. The Ocular Epidemiology Reading Center at the University of Wisconsin-Madison (47) will grade the images for presence and severity of diabetic retinopathy (DR), macular edema and will make measurements of retinal vessel calibers. After grading the retinal images from the 2nd retinal visit, a separate longitudinal review will be conducted to confirm progression/regression status of diabetic retinopathy or macular edema severity.

Table 4. Data Collected on Cohort Study Participants						
Variables	Baseline Visit (C0)	12, 24, 60 months	SEARCH 3 Visit (C ₁)	SEARCH 4 Visit (C2)		
Surveys:						
Demographics: Sex, Race/ethnicity, Parental age	X					
Employment, education: parent or youth > 18 years		Х	X	Х		
Medical Record: Diabetes type, date of diagnosis	Х					
Health History: Birth date & weight, age at onset	Х					
Pubertal status, co-morbidities; family history	Х	Х	Х	Х		
Pregnancy outcomes in females				Х		
Medication: Diabetes & related conditions	Х	Х	Х	Х		
Behavioral: Diet, physical activity, alcohol use	Х	Х	Х	X		
Marijuana, other substance use				Х		
Processes of care/quality of care			Х	X		
Health care costs			Х	X		
Psychosocial: Depression (CES-D)	Х	Х	Х	Х		
Family conflict; fear of hypoglycemia			Х	X		
Transitions of care			Х	X		
Food security and assistance				X		
Stressors; work ability index; stigma/discrimination				Х		
Physical exam: BMI, waist , blood pressure, acanthosis	Х	Х	Х	X		
Laboratory measures (blood):				1		
Autoantibodies	X	X	X			
Fasting glucose, cystatin C, serum creatinine, fasting C-peptide, lipid profile, inflammatory markers (CRP, IL6), A1c, AGE (CML), DNA, miRNA extraction	Х	X	X	X		
URINE: albumin, creatinine (spot)	Х	Х	Х			
URINE: albumin, creatinine (first morning void)			Х	Х		
Stored Samples: DNA, miRNA, serum, plasma, urine	Х	Х	X	Х		
Outcome(s):			-			
Cardiovascular: Arterial stiffness (PWV, AiX)	Х		X	Х		
Cardiac echocardiography: LV mass, systolic & diastolic function				Х		
Neuropathy: heart rate variability; peripheral neuropathy		X (pilot)	X	Х		
Retinopathy Retinal photos, vessel caliber		X (pilot)	Х	Х		
Nephropathy: Albuminuria	Х	X	Х	Х		
Cystatin C		Х	Х	Х		
Neurocognitive tests: NIH Toolbox.				Х		
Acute complications: DKA, hypoglycemia	Х	Х	Х	Х		
Quality of life (Peds QL3.2 Diabetes Module)	Х	Х	Х	Х		
Mortality surveillance (NDI)	Х	Х	Х	Х		

Measures of Kidney Function

Urine albumin:creatinine ratio: We will collect first morning void (FMV) urine samples for storage and calculation of urine albumin:creatinine ratio (UACR). We will request a second FMV sample in the case of a positive urine for microalbuminuria (UACR \geq 30µg/mg), or if a urine sample is rejected due to possible contamination (positive leukocyte esterase and/or nitrite). In previous phases we had collected random urine samples (with the addition of the FMV at SEARCH 3).

Estimated glomerular filtration rate: Equations with the most accurate and precise estimation of glomerular filtration rate (GFR), utilize both serum creatinine and cystatin C (48, 49). Both tests have been measured in SEARCH 1-3 and continue to be measured in SEARCH 4. Different equations are currently used in children versus adults, and on the expected range of GFR (hyperfiltration versus normal GFR versus low GFR) (48-51). The natural history of eGFR in diabetic kidney disease can be heterogeneous and so we will also investigate the optimal equations for use in children versus adults and at different spectrums of GFR.

Measures of Neuropathy

Peripheral Neuropathy: The Michigan Neuropathy Screening Instrument (MNSI) will be used to screen for the presence of diabetic neuropathy. It consists of 15 self-administered questions on foot sensation including pain, numbress and temperature sensitivity. The second part of the MNSI is a brief physical examination involving 1) inspection of the feet for deformities, dry skin, hair or nail abnormalities, callous or infection, 2) semiquantitative assessment of vibration sensation at the dorsum of the great toe, 3) grading of ankle reflexes and 4) monofilament testing. Patients screening positive on the clinical portion of the MNSI (greater than 2 points on a 10 point scale) are considered neuropathic.

Cardiac Autonomic Neuropathy: Heart rate variability (HRV) analysis allows us to assess the autonomic nervous system by examining sympathetic balance, which raises heart rate and blood pressure and causes vasoconstriction, and the parasympathetic balance which has opposite effects (52,53). Assessments use a SphygmoCor SCOR-CPV device (AtCor Medical, Australia) as performed previously (54).

Arterial stiffness. Pulse wave velocity (PWV) is measured using the SphygmoCor (55). The average of 3 ECG R-wave gated arterial waveforms are recorded from the carotid and then the femoral arteries. Augmentation index (Aix) is measured with the same device (56).

Neurocognitive tests. Neurocognitive measures are computer administered utilizing the NIH Toolbox (57); domains include attention, verbal skill, working memory, mental flexibility, episodic memory, speed of processing, and response inhibition. These areas were chosen to reflect both more generalized (depressed psychomotor speed) and distinct areas of deficit (memory, attention, and mental flexibility). Receptive language vocabulary is used as a proxy for educational attainment/premorbid functioning.

Acute complications. Acute complications studied are severe hypoglycemia and diabetic ketoacidosis (DKA). Severe hypoglycemia is defined as a hypoglycemia event requiring assistance of another person (58). For DKA, occurrence is recorded as emergency department visit or hospitalization. This aligns well with prior publications on acute complications, and data frequently recorded in patient surveys and medical records (59).

Mortality Surveillance. All centers will systematically identify deaths that occur between the date of diagnosis and December 31, 2017 among youth in the 2002-2015 incident cohorts. The National Death Index will serve as the primary data source, plus individual case reports of deaths made to the study team during the course of the study.

5. Development and Validation Projects

The recent implementation of robust EHR systems throughout the US provides opportunities to substantially enhance the efficiency of surveillance and to pilot expansion of the SEARCH Registry beyond the currently funded sites. SEARCH 4 will attempt to optimize efficiency of SEARCH surveillance activities through targeted Development and Validation (D&V) Projects designed to utilize electronic health data to operationalize each of the three tiers of surveillance. Methods will employ electronic algorithms and text mining/natural language processing with validation, incorporating data from administrative records, medical records including provider notes, pharmacy, and laboratory data. We will then evaluate these approaches with a goal of identifying a model for targeted expansion of the SEARCH Registry to non-SEARCH sites.

Four of the five SEARCH centers are part of networks funded by Patient-Centered Outcomes Research Institute (PCORI)'s multi-institutional clinical data research networks (CDRN) formed in 2014. Three of the centers, OH, WA, and CO, are part of "A National Pediatric Learning Health System Network" (PEDSnet). The fourth clinical center, CA, is part of "Kaiser Permanente & Strategic Partners Patient Outcomes Research to Advance Learning" (PORTAL) Network. In South Carolina, a new entity, Health Sciences South Carolina (HSSC), has been establishing a data warehouse to bring together EHR data from at least four of the six major provider systems from which cases are ascertained for the Carolina site.

This work will follow a three-step process to include development, validation and implementation. First, new approaches will be developed and initially validated through the D&V Projects in limited locations. For each approach, the established SEARCH processes for case ascertainment, case validation, and determination of diagnosis date, diabetes type, and key clinical and demographic data will be considered the "gold standard" against which new approaches will be compared. Second, approaches that meet appropriate initial validation criteria will be further refined and validated at additional SEARCH centers. Third, implementation as part of ongoing SEARCH Registry work will occur only after pre-determined metrics (e.g., sensitivity, specificity, PPV) are demonstrated for each EHR system in which the approach is to be implemented.

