6.2. COHORT STUDY - STATISTICAL CONSIDERATIONS

6.2.1. Aim 1: Burden of Complications

Three main analytic approaches will be employed to examine the prevalence, incidence, progression and clustering of complications by diabetes type and responsible risk factors and pathways: a) estimating incidence and prevalence using multiple logistic regression methods; b) estimating the progression of complications using longitudinal mixed models; and c) estimating the clustering of risk factors and outcomes using longitudinal mixed models. For each of these approaches we will incorporate participant level characteristics, measured at multiple time points, to examine potential mediators and moderators of outcomes.

Incidence Rate Estimation: Participants have had at least two previous in-person visits (C_0, C_1) ; however, for many outcomes (retinopathy, neuropathy, etc.) participants will have had only one previous assessment (C1 visit). For these outcomes we will be able to define a group of participants who were free from the event of interest (e.g. no retinopathy) at C1. Multiple logistic regression methods will be employed to examine the incidence rates of binary measures, with categorical (e.g.T1D vs. T2D) or continuous (e.g. A1c) predictors. We will evaluate potential confounding and/or effect modification based on our extensive databases.

Prevalence Rate Estimation: Some of the outcomes of interest have not been measured previously (e.g. echocardiography); therefore, we will estimate the prevalence of these outcomes. Associations of risk factors and diabetes type with prevalent outcomes will be examined using logistic regression models.

Statistical Power: For each of the primary dichotomous outcomes of interest (incidence or prevalence) we estimated proportions that will have the specific outcomes of interest, based on data from the C₁ visit. Table 6 shows the expected sample sizes available for comparing T1D and T2D, the corresponding detectable differences in rates, and the power for each outcome. We also provide the expected detectable differences in prevalence rates of LV hypertrophy between T1D and T2D in the sample of patients receiving echocardiography. These calculations are performed using Fisher's exact tests with $\alpha = 0.05$ (2-sided).

Table 6. Power for detectable differences for primary outcomes								
Outcome	T1D/T2D available	T1D rate	T2D rate	Power				
	Incidence Comparisons							
Retinopathy	1215/230	10%	18%	88%				

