Neuropathy	1344/283	5%	10%	81%				
Nephropathy	1172/268	20%	29%	85%				
Prevalence Comparisons (Cardiac echocardiography)								
LV hypertrophy	250/250	5%	13%	86%				

Longitudinal Models: We will use a longitudinal mixed effects analysis of covariance approach to make comparisons among groups which includes duration of diabetes as a time-varying covariate and participant as a random effect. This approach models the varying durations of disease prior to the initial visit, and the varying durations of time allowed by the data collection windows between visits. These mixed effects models are flexible to allow for non-linear relationships to be modeled over time, and permit random rates of progression.

To estimate the sample size needed to detect a significant difference with sufficient power, calculations were based on comparing measurements after adjusting for C_0 or C_1 data. If the correlation between measurements is moderate (0.50) then we have 80% power to detect a difference of 0.139 standard deviations (SD) for each outcome of interest. For example, based on data collected on a subset of SEARCH T1D participants, the standard deviation for PWV carotid-femoral was estimated to be 0.7 m/s, thus we would have 80% power to detect a difference of 0.10 m/s in progression of PWV between youth with T2D vs T1D.

Clustering of Outcomes: In addition to examining each endpoint separately, we have the opportunity to look simultaneously at several outcomes in the same analysis. We

will create variables that describe the co-occurrence (clustering) of outcomes for each participant and examine whether there are differences in the patterns of these clusters between T1D and T2D youth. Approaches will utilize ordinal logistic regression methods or longitudinal mixed models depending on whether the clustering outcome is a count or categorical. More sophisticated statistical methods may also be used such as principal components analyses to determine which risk factors may form different components.

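### The named primary echocardiographic measure, continuous LV mass, has no matching analysis or power; the protocol analyses echocardiography only as a prevalence and powers only LV hypertrophy

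*Protocol*

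**What the plan says.** In the protocol's section 4.2, the echocardiography paragraph lists several readings and singles one out: "The primary outcome measure is LVM determined by 2-D guided M-mode echo at end diastole". Table 4 gives the same outcome, "Cardiac echocardiography: LV mass, systolic & diastolic function", and marks it at the SEARCH 4 visit (C2) only.

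Section 6.2.1 takes a different outcome. Under prevalence estimation it says: "Some of the outcomes of interest have not been measured previously (e.g. echocardiography); therefore, we will estimate the prevalence of these outcomes". The model follows: "Associations of risk factors and diabetes type with prevalent outcomes will be examined using logistic regression models". On power it says: "We also provide the expected detectable differences in prevalence rates of LV hypertrophy between T1D and T2D". The one echocardiographic row of Table 6 is LV hypertrophy, 250 T1D and 250 T2D, 5% against 13%, power 86%, by a two-sided Fisher's exact test at 0.05.

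The only power statement for a continuous outcome in Cohort Aim 1 is in the longitudinal-models paragraph of section 6.2.1: 0.139 SD at 80% power, with correlation 0.50, after adjustment for C0 or C1 values.

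**The concern.** The outcome called primary and the outcome that is analysed and powered are not the same. LVM is a measured quantity; LVH is a yes/no state, presumably derived from it by a rule the protocol does not give. Of the three analytic approaches listed at the start of section 6.2.1, one is logistic regression and the other two are longitudinal mixed models. None is a model for a continuous outcome measured once.

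Two things are at stake. A reader cannot tell which result is the main echocardiographic one. And if only LVH is analysed, the sub-study gives up much of the information in the measurement it calls primary, which matters most for moderate differences between diabetes types.

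**Working it through.** **Inputs from the protocol.** LVH 5% (T1D) and 13% (T2D), 250 per group, Fisher's exact test, two-sided 0.05 (section 6.2.1, Table 6). Echo sample 500, as 250 + 250, in the text of section 3.3.2, but 450 in its site table, with no split by type. Echo at C2 only (Table 4).

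**Assumptions.** The protocol gives no SD for LVM and no cut-point for LVH. I take LVM as normal with equal SD in both groups and one common cut-point. For 450 I take 225 per group.

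**1. The plan's own figure.** Summing the two-sided Fisher rejection probability over both binomial distributions at 250/250, 5% against 13%, gives 86.3%. The stated 86% reproduces. At 225/225 it is 82.0%; at 250/200, split either way, 83% to 84%.

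**2. Does the 0.139 SD statement cover echocardiography?** The formula is (1.960 + 0.842) × √[(1 − 0.5²)(1/n₁ + 1/n₂)]. Taking the 382 T2D participants used in section 6.2.2, and 1846 − 382 = 1464 T1D, it gives 2.802 × √[0.75 × (1/1464 + 1/382)] = 0.139. The figure therefore matches the full set of 1846 visits, and it needs an earlier measurement. It does not describe the echo sample.

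**3. The LVM shift implied by Table 6.** z(0.95) − z(0.87) = 1.645 − 1.126 = 0.518 SD.

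**4. Power for LVM at that shift.** Φ(0.518/√(2/n) − 1.960):
- n = 250: Φ(5.80 − 1.96) = 99.99%
- n = 225: Φ(5.50 − 1.96) = 99.98%

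**5. Sample size per group for 86% power at 5% against 13%.**
- LVM: 2 × (1.960 + 1.080)²/0.518² = 69
- LVH: [1.960 × √(2 × 0.09 × 0.91) + 1.080 × √(0.05 × 0.95 + 0.13 × 0.87)]²/0.08² = 235

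The ratio is 69/235 = 29%, a loss of about 70%. As a cross-check, the large-sample efficiency of a dichotomised normal variable, φ(c)²/[p(1 − p)], is 22% at p = 5%, 32% at 9% and 40% at 13%.

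**6. Range of shifts.** T1D prevalence is held at 5%, and T2D prevalence follows from the shift. LVH power is by Fisher's exact test, LVM power by the t-test.

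| Shift (SD) | T2D LVH | LVH, 250/250 | LVM, 250/250 | LVH, 225/225 | LVM, 225/225 |
|---|---|---|---|---|---|
| 0.20 | 7.4% | 16% | 61% | 14% | 56% |
| 0.25 | 8.2% | 24% | 80% | 21% | 75% |
| 0.30 | 8.9% | 35% | 92% | 31% | 89% |
| 0.40 | 10.7% | 61% | 99% | 55% | 99% |
| 0.52 | 13.0% | 86% | >99.9% | 82% | >99.9% |

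**7. Detectable LVM difference at 80% power.** 2.802 × √(2/250) = 0.25 SD; 2.802 × √(2/225) = 0.26 SD. Both are unadjusted, as is the Fisher calculation in Table 6.

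**The case against.** LVH prevalence is a fair target. Cohort Aim 1 concerns the burden of complications, and hypothesis 1.1 predicts higher prevalence in T2D. For an outcome seen once, the prevalence of an abnormal state answers that directly, whereas a difference in mean LVM does not. That stands, and it is why LVH should stay in the plan.

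The two sections can also be read together. Section 4.2 is about measurement, LVH is a classification based on LV mass, and the Table 6 calculations are presented as those for dichotomous outcomes, so a continuous row would not be expected there. This explains how the mismatch arose but does not remove it. Section 4.2 uses the words for a primary outcome, and section 6.2.1 names echocardiography specifically when it assigns prevalence estimation and logistic regression.

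A statistical analysis plan, not available here, may contain an LVM model. Transformation and the exact form of body-size adjustment can properly sit there. The point is not that such detail is absent: the analysis the protocol does state is for a different outcome from the one it names.

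Two stronger readings are tempting. A reader might infer that the sub-study throws away most of its power. The documents do not support that: at the plan's own target, power for LVH is 86%, or about 82% at 225/225. A reader might also infer that there are too few LVH events for the adjustment hypothesis 1.1 requires. Expected events are 250 × 0.05 + 250 × 0.13 = 45, or about 40 at 225/225, but the protocol sets no criterion for events per model term, so this cannot be called an error.

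**Conclusion.** The point holds as a mismatch between the named primary echocardiographic measure and the only analysis and power stated for echocardiography. It is not a finding of inadequate power for LVH.

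The cost of analysing LVH alone is about 70% of the effective sample size. At the shift implied by 5% against 13% this is affordable. At about 0.30 SD or less it removes most of the power: at 250/250, 24% against 80% at 0.25 SD and 35% against 92% at 0.30 SD. The protocol does not set shifts of that size as targets.

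The comparison rests on normal LVM, equal SDs and one common cut-point, and would change if LVM is skewed or if LVH is defined by different thresholds in subgroups. The 225/225 figures also assume an even split of 450. The difference between 500 and 450 in section 3.3.2 is a separate matter to reconcile. The mismatch itself depends on none of these assumptions.

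**What to change.** In section 6.2.1:
- Add, as the analysis of the named primary echocardiographic measure, a linear regression of LVM, accounting for body size, on diabetes type, adjusted for age, sex, diabetes duration and race/ethnicity as hypothesis 1.1 requires.
- Add a power line for it: at 80% power the detectable difference is 0.25 SD at 250/250, or 0.26 SD at 225/225. State that these are unadjusted, and on which LVM scale the SD is taken.
- Keep the LVH prevalence comparison by logistic regression alongside it as the dichotomous outcome, and state how LVH is derived from LVM.

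The cost is one more analysis and one power line. No new data are needed, and nothing already planned is lost.
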